H1. Compared with usual management, self-management of urinary symptoms with probiotics will reduce the frequency, severity and impact of urinary symptoms and UTIs (PRIMARY OUTCOMES). The goal of aim 2 is to assess the effect of *Lactobacillus* supplementation on the frequency, severity and impact of urinary symptoms and UTIs. This aim can be evaluated with all 100 participants in the SMP pilot study. We expect to find a significant difference in these primary outcomes between our three experimental timeframes (6 months prior to intervention, 6 months of SMP_{PRO} intervention, and 6 month follow-up period). Frequency of UTI will be defined as the number of verified UTIs occurring during the timeframe. Urinary symptoms will be assessed using the USQ-NB where frequency of symptoms, degree of severity, and impact on the individual, will be considered.

We will estimate the average number of symptoms on the USQ-NB endorsed (irrespective of frequency, severity and impact) across the weeks during that time frame, for each participant. Thus, each participant will have a continuous outcome (average number of USQ-NB items endorsed). We will also compute the number of verified UTIs experienced by each participant. These two outcomes are the primary outcomes for our study and analysis; they depend solely on the face validity of the USQ-NB, and on clinically verified UTIs, and so will not be affected by a failure to find or establish formal measurement properties for the USQ-NB, should any occur. They will also be less subject to any variability in participant perceptions of frequency, severity or impact, which can complicate analytic assumptions and limit power and interpretability of change that might be perceived. We will describe these features of the sample over time but will not conduct inference tests on these ratings.

We propose linear mixed-effects modeling to explore the effect of introduction to/use of the SMP_{PRO} on the number of USQ-NB symptoms (averaged over the entire time frame) and the incidence of UTIs. Each model will include gender as a fixed effect, and time (baseline; SMP_{PRO} use; post-SMP_{PRO} observation) as the explanatory variable, and random effects for intercept (subject) only. This method allows for missing data and the inclusion of covariates where appropriate; however we plan post-hoc analyses of the modeling in order to pinpoint potential interaction effects (e.g., between age or sex and time). The focus of the analyses is to determine whether (irrespective of individual starting values or specific slopes) mean USQ-NB item endorsement and UTI counts go down in the SMP_{PRO} time frame relative to the baseline values (generally negative associations in each regression between the outcome and time) and whether these values stay flat (zero slope), continue to decrease (negative slope) or increase (positive slope) during the post-SMP_{PRO} follow up.

Power calculation: We plan to use mixed effects regression modeling for the most precision in our estimated effects of the SMP_{PRO} on the USQ-NB symptom rate and UTI rate. However, it is difficult to predict the exact form of the final models since our understanding of the USQ-NB symptom makeup, and the univariate associations between gender or age (or any other of the demographic variables we will collect) and these two outcomes. Therefore, for the most conservative estimates, we use the most basic analytic method to estimate the worst-case scenario power calculation, a t-test. In this pair of primary outcomes, alpha is set at 0.025 for each power calculation (and for each inference test). We will have data from 100 participants; however, to protect against a possible 20% drop out rate over the course of the 18-month study, we will recruit 120 persons for this arm, hoping for a final N of 100. If we observe an average of 25 items on the USQ-NB endorsed over the baseline period, then with alpha = 0.025 we would have 81% power to detect a reduction in this average number of items endorsed as low as five

The Impact of Self-Management with Probiotics on Urinary Symptoms and the Urine Microbiome in Individuals with Spinal Cord Injury and Spina Bifida Protocol
5/18/2017

(i.e., to detect a change from an average of 25 to an average of 20) during the SMP_{PRO} period, assuming that the standard deviation of the average number of endorsed USQ-NB items is as high as 16. If we observe an average of one UTI per month in the initial 6-month period (for an average of six UTIs across this sample of 100 persons), then, with the alpha of 0.025 we would have 81% power to detect a reduction in this average number of UTIs as low as 1.25 (i.e., to detect a change from an average of 6 to an average of 4.75) during the SMP_{PRO} period, assuming that the standard deviation of the number of UTIs is as high as 4. We will explore the consistency of the UTI variable with the assumption of a normal distribution, and if appropriate we may utilize Poisson modeling if the assumption of normality is violated.

Additionally, because we have the potential to carefully describe the symptom profile for neuropathic bladder generally and for SCI/MS and SB specifically, we also plan secondary analyses based on the USQ-NB items. Frequency, severity, and impact of each of the USQ-NB symptoms will be estimated for each participant, within each of the study timeframes. Each of these symptom characteristics will be rated on an ordinal scale, so *for each symptom* on the USQ-NB, the median frequency rating from their weekly USQ-NBs will be computed. These ordinal outcomes will be explored for similarities and differences across sex, age, injury (SB/SCI/MS), and other demographic variables that could be useful in diagnosis or management of USQ-NB symptoms by us and other investigators in future studies. Descriptive statistics for each primary outcome (frequency, duration, and severity of each UTI) and their change from baseline, will be produced for each time frame. We will generate preliminary (underpowered and not corrected for multiple comparisons) estimates of the strengths of associations between item frequency, severity, and impact with time, sex, age, satisfaction with the SMP-UTI, and etiology (SCI/MS/SB). If the reliability and validity evidence from Aim 1 and that national sample supports the estimation of latent factor scores on the USQ-NB factors, we will also compute preliminary estimates of association between these covariates and the factor scores, as well as the association between the SMP-UTI and changes in these factor scores. This estimation will only be appropriate if measurement invariance across groups is obtained in Aim 1, but since we would not yet have evidence of invariance over time, these estimates would be considered preliminary.

H2. Compared with usual management, self-management of urinary symptoms with probiotics will reduce bladder inflammation (Secondary outcome). For those 20 participants in the subsample giving urine samples, bladder inflammation will be measured from each urine sample using a standard white blood count (WBC) from the urinalysis. WBC counts will be obtained only at the start of each timeframe, and so can be analyzed longitudinally as continuous variables representing the 6-month pre-treatment period and the 6 month-SMP_{PRO} period. As such we plan a mixed effects linear regression model of WBC counts with time treated as the factor of interest. This analysis will assess whether WBC is significantly different from the SMP_{PRO}, and post-SMP_{PRO}, relative to the baseline pre-treatment periods.

H3. Compared with usual management, self-management of urinary symptoms with probiotics will reduce the need for antibiotics to treat UTI (Secondary outcome). The number of times antibiotics are used for each patient will be obtained from their medical records or self report. This value will be analyzed with the same three-point longitudinal mixed effects regression model with time as the factor of interest. Depending on the distribution of the outcome (i.e. given the count nature of this outcome, it may be Poisson distributed), we will utilize either linear or Poisson regression models. This analysis will assess whether there is an association between UTI rate during use of the SMP_{PRO}, and post-SMP_{PRO} exposure, relative to UTI rate during the baseline pre-treatment period.

H4. Compared with usual management, self-management of urinary symptoms with probiotics will return the microbiome to baseline (Secondary outcome). For analysis of the microbiome, the fasta and fastq files of each sample's CCS reads will be retrieved and processed using LUCY⁵⁴ to filter out reads with low quality segments, as well as remove sequences that are shorter than the full length 16S rRNA (approximately 1500 bp). The sequences will then be aligned against the SILVA 16S rRNA database followed by subsequent implementation of Mothur's Chimera Slayer to filter out chimeric reads from sequences in each sample. The remaining sequences will undergo taxonomic classification. Bowtie2 will align each sequence read to a reference genome derived from the SILVA 16S database and output a SAM file. With the resulting SAM file, Pathoscope⁵¹ is capable of characterizing the biological sample to the subspecies-level, generating an excel file with the proportions of each classified organism within the sample tabled.

To determine whether bacterial diversity differs between study groups the Shannon Diversity Index will be used. The Shannon Index is a measure of sample diversity that takes into account total number of bacterial types in the sample and relative proportion of the bacterial types. From the subsample of 50 participants giving urine samples, subjects who did in fact utilize the SMP at least once during the 6-month SMP time frame will be stratified into two groups, those who responded to SMP and those who did not; we will define "response" as the observation of a 10% or more decrease in the average number of USQ items endorsed within any time frame, so that each of the 50 persons in this sub-sample will be characterized as either a responder (10% or more decrease) or a non-responder (0-9.99% decrease). A scatter plot of response group versus Shannon Index will be produced, and a mixed effects linear regression model will test the individual (main) and interaction effects of response group and time on Shannon Index. A positive time coefficient is indicative of increased microbiome diversity and a negative time coefficient indicates reduces diversity. The magnitude of difference between the response groups will be determined using the Yue-Clayton theta similarity index (θ). The θ index measures the difference in the number and relative abundance of bacterial species between samples^{4,5} when $\theta=1$ two samples have identical community structure and when $\theta=0$ indicates complete dissimilarity between samples. Pathoscope will be used to calculate abundance of different taxonomic groups at each time point.

REFERENCES

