Phase Ia: Safety study of a single bladder instillation of probiotic in adults. A subsample of healthy adults with neuropathic bladder who do not have urinary symptoms meeting the criteria for antibiotic treatment of urinary tract infection or initiation of the protocol will undergo a single intravesicular instillation of *Lactobacillus* to determine the tolerability of the instillation, safety of a single instillation, and whether the instilled *Lactobacillus* persists in the urine.

Study Design: We will recruit N=5 adult subjects with neuropathic bladder due to SCI or SB.

Clinical Setting: MedStar National Rehabilitation Hospital

The Impact of Self-Management with Probiotics on Urinary Symptoms and the Urine Microbiome in Individuals with Spinal Cord Injury and Spina Bifida Protocol

5/18/2017

Page 1 of 17

Target Enrollment: 5 subjects at least 18 years of age with SCI or SB and at least 1-year post-injury (if SCI).

Informed Consent: Consent will be obtained by the PI, Study Coordinator, or Research Assistant.

Inclusion Criteria: Inclusion criteria for safety study participants are: 1) age 18-50 years; 2) if SCI, at least 1-year duration; 3) neuropathic bladder, as determined by the attending physician; 4) utilizing intermittent catheterization for bladder management; and 5) community dwelling.

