will be presented to the DSMB. Phase 1b will be initiated only after review and approval of the Phase 1a safety data by the DSMB. Once approval demonstrates that a single dose of intravesicular *Lactobacillus* has been determined to be safe in adults, the same safety study will be repeated in children. A subsample of healthy children with neuropathic bladder due to SB who do not have urinary symptoms meeting the criteria for antibiotic treatment or initiation of the protocol will undergo a single intravesicular instillation of *Lactobacillus* to determine the tolerability of the instillation, safety of a single instillation, and whether the instilled *Lactobacillus* persists in the urine.

Study Design: We will recruit N=5 children with neuropathic bladder due to SB or SCI.

Clinical Setting: MedStar National Rehabilitation Hospital and Children's National Medical Center.

Target Enrollment: 5 subjects at least 6 years of age with SB or SCI, at least 1-year post-injury (if SCI).

Informed Consent: Consent and assent will be obtained by the PI, Study Coordinator, or Research Assistant.

Inclusion Criteria: Inclusion criteria for safety study participants are: 1) age ≥ 6 years; 2) if SCI, at least 1-year duration; 3) neuropathic bladder, as determined by the attending physician; 4) utilizing intermittent catheterization for bladder management; and 5) community dwelling.

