Recruitment Strategy: SCI/MS and SB subjects will be enrolled with assistance from United Spinal Association. Additionally, we will query the MedStar National Rehabilitation Hospital inpatient service, the 40+ MedStar National Rehabilitation Network outpatient sites, various MedStar Network databases, and Children's National Medical Center (CNMC) SB database.

Databases will be queried for participants who meet the eligibility criteria and have already *The Impact of Self-Management with Probiotics on Urinary Symptoms and the Urine Microbiome in Individuals with Spinal Cord Injury and Spina Bifida Protocol*

5/18/2017

provided HIPAA authorization and consent to be contacted for future research. Announcements and IRB-approved flyers will be posted on the United Spinal Association and study websites and at participating institutions.

Informed Consent: Informed consent will be emailed or mailed (if not in person at MedStar NRH or CNMC) out to participants interested in the study. Paid return envelopes will be included for participants to return signed informed consent to Study Coordinator. At MedStar NRH and CNMC, consent will be obtained by the PI, Study Coordinator, or Research Assistant.

Inclusion Criteria: Inclusion criteria for participants with SCI/ MS includes: 1) age \geq 18 years; 2) SCI/MS; 3) neuropathic bladder at least 1 year duration, as determined by the attending physician; 4) utilizing intermittent catheterization for bladder management; 5) a history of 2 or more UTIs in the past year; and 6) community dwelling. Inclusion criteria for participants with SB adults includes: 1) age \geq 18 years; 2) SB; 3) neuropathic bladder as determined by the attending physician; 4) utilizing intermittent catheterization for bladder management; 5) a history of 2 or more UTIs in the past year; and 6) community dwelling. Inclusion criteria for pediatric subjects includes: 1) age \geq 6 years; 2) SB or SCI; 3) neuropathic bladder at least 1 year duration (for SCI), as determined by the attending physician; 4) utilizing intermittent catheterization for bladder management; 5) a history of 2 or more UTIs in the past year; and 6) community dwelling.

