Exclusion Criteria: Study candidates with the following will be excluded: 1) known genitourinary pathology beyond neuropathic bladder (i.e., vesicoureteral reflux, bladder or kidney stones, etc.); 2) use of prophylactic antibiotics; 3) instillation of intravesicular agents to reduce UTI (i.e., gentamycin); 4) psychologic or psychiatric conditions influencing the ability to follow instructions; 5) participation in another study in which results would be confounded; 6) pregnant or breastfeeding; 7) individuals with a history of acquired or genetic immunodeficiencies; active, acute or chronic serious infections (i.g., viral hepatitis, HIV/AIDs); 8) individuals with cancer/autoimmune disorders; 9) serious allergy to any component or excipients in the live bacterial combination product; 10) no change in neurologic status in the previous 2 weeks; 11) taken antibiotic for any reason in the previous 2 weeks; 12) any patient with history of sensitivity or allergy to ampicillin or tetracycline; and 13) current urinary tract infection or urinary tract infection within the previous 2 weeks (as defined by Infectious Diseases Society of America CAUTI Guidelines, 2010. According to the Infectious Disease Society of America Guidelines for Diagnosis of Catheter-Associated UTI, the presence of the following urinary symptoms is required for UTI diagnosis in patients using intermittent catheterization: new onset or worsening fever, rigors, altered mental status, malaise, lethargy with no other identified cause, flank pain, costovertebral angle tenderness, acute hematuria, pelvic discomfort, increased spasticity, autonomic dysreflexia or sense of unease. The Guidelines specifically state that “the presence or absence of odorous or cloudy urine should NOT be used as an indication for urine culture or antimicrobial therapy” and “the presence, absence or degree of pyuria should NOT be interpreted as an indication for antimicrobial treatment.” If a subject presents with any of these symptoms and there are $\geq 10^3$ cfu/hpf bacterial growth on urine culture, the subject will be excluded and treated for a UTI according to clinical best practice.

Baseline Data Collection: After consent, participants will complete the Health History Questionnaire. Thereafter, participants will complete the Urinary Symptom Questionnaire (USQ-NB) weekly.

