Inclusion criteria for participants with SCI/SB/MS includes: 1) age \geq 18 years; 2) SCI/SB/MS; 3) neuropathic bladder at least 1-year duration, as determined by the attending physician; 4) utilizing intermittent catheterization for bladder management; 5) a history of 2 or more UTIs in the past year; 6) community dwelling, 7) Enrollment in Phase II

Exclusion Criteria: Study candidates with the following will be excluded: 1) known genitourinary pathology beyond neuropathic bladder (i.e., vesicoureteral reflux, bladder or kidney stones, etc.); 2) use of prophylactic antibiotics; 3) instillation of intravesicular agents to reduce UTI (i.e., gentamycin); 4) psychologic or psychiatric conditions influencing the ability to follow instructions; 5) participation in another study in which results would be confounded; 6) pregnant or breastfeeding; 7) individuals with a history of acquired or genetic immunodeficiencies; active, acute or chronic serious infections (i.g., viral hepatitis, HIV/AIDS); 8) individuals with cancer/autoimmune disorders; 9) serious allergy to any component or excipients in the live bacterial combination product; 10) no change in neurologic status in the previous 2 weeks; 11) taken antibiotic for any reason in the previous 2 weeks; 12) any patient with history of sensitivity or allergy to ampicillin or tetracycline; and 13) current urinary tract infection or urinary tract infection within the previous 2 weeks (as defined by Infectious Diseases Society of America CAUTI Guidelines, 2010 14) Not enrolled in Phase II. According to the Infectious Disease Society of America Guidelines for Diagnosis of Catheter-Associated UTI, the presence of the

The Impact of Self-Management with Probiotics on Urinary Symptoms and the Urine Microbiome in Individuals with Spinal Cord Injury and Spina Bifida Protocol

5/18/2017

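### Item 10 in all four exclusion lists is worded in the opposite direction to its lead-in, so read literally it excludes neurologically stable candidates

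*Combined protocol and SAP*

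**What the plan says.** The combined protocol and SAP has a separate Exclusion Criteria paragraph for Phase Ia, Phase 1b, Phase II and Phase III. Each opens with the same lead-in, "Study candidates with the following will be excluded", and each has the same tenth item: "10) no change in neurologic status in the previous 2 weeks".

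Two other items in each list use a 2-week window. One is "11) taken antibiotic for any reason in the previous 2 weeks". The other, numbered 13 (12 in Phase 1b), is "current urinary tract infection or urinary tract infection within the previous 2 weeks".

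The people sought are described elsewhere. Phase Ia takes "A subsample of healthy adults with neuropathic bladder who do not have urinary symptoms" of a kind that would call for treatment, and Phase 1b takes "A subsample of healthy children with neuropathic bladder due to SB". The Phase II inclusion list for adults with SCI or MS asks for "neuropathic bladder at least 1 year duration, as determined by the attending physician", and Phase III asks for "neuropathic bladder at least 1-year duration, as determined by the attending physician". Every inclusion list requires community dwelling.

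**The concern.** An exclusion list works by naming what disqualifies a candidate. Item 10 names the absence of a change, so under its lead-in it disqualifies the stable candidate. It has the form of an inclusion requirement placed in the wrong list.

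This is an operative eligibility rule, repeated in every phase, and it is the only criterion in any list that deals with recent neurologic change. Followed as written, it would turn away stable candidates and pass those with a recent change. Read in reverse, as staff probably would, it leaves each stable person enrolled meeting a written exclusion. Either way, screening staff cannot take the rule from the text; they have to infer it.

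**Working it through.** The plan gives no figure on this point, so there is nothing to reproduce. The check is a comparison of texts.

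**Step 1: what item 10 does under its lead-in.** The lead-in excludes a candidate when the item is true of that candidate.

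| Candidate's last 2 weeks | Item 10 true? | Literal result | Result if read in reverse |
|---|---|---|---|
| Neurologic status unchanged | Yes | Excluded | Passes item 10 |
| Neurologic status changed | No | Passes item 10 | Excluded |

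The two readings give opposite answers for every candidate.

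**Step 2: item 10 against the rest of its list.**

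| List | Items | Stated as an absence | 2-week items | Of these, exclude on a recent event |
|---|---|---|---|---|
| Phase Ia | 13 | 10 | 10, 11, 13 | 11, 13 |
| Phase 1b | 12 | 10 | 10, 11, 12 | 11, 12 |
| Phase II | 13 | 10 | 10, 11, 13 | 11, 13 |
| Phase III | 14 | 10, 14 | 10, 11, 13 | 11, 13 |

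Items that name a disqualifying condition or event: 13 − 1 = 12, 12 − 1 = 11, 13 − 1 = 12 and 14 − 2 = 12. Phase III item 14 is negative for good reason. It shuts out people who are not in Phase II, and inclusion item 7 of the same phase requires Phase II enrolment, so the two agree. Item 10 has no such counterpart. In each list, two of the three 2-week items exclude on a recent event, and item 10 alone excludes on the lack of one.

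**Step 3: is the direction settled elsewhere?** The inclusion lists (one each for Phases Ia, 1b and III, three for Phase II) cover age, diagnosis, duration, catheterization, community dwelling and, in Phases II and III, UTI history; Phase III adds Phase II enrolment. None mentions neurologic status. No other section rewords or explains item 10.

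**Step 4: does the described population settle it?** Only indirectly.
- The 1-year rule is partial. In Phases Ia and 1b it applies to SCI only. In Phase II it applies to adults with SCI or MS and to children with SCI, but not to adults with SB. In Phase III it applies to everyone.
- A person can live in the community, have had the condition for over a year, and still have had a neurologic change in the past 2 weeks.
- In the Phase Ia and 1b descriptions, the word healthy is tied to having no urinary symptoms that would trigger treatment. It says little about neurologic stability.

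These descriptions make the literal reading implausible, because it would bar most of the people described. They do not logically exclude it.

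**Step 5: does it reach the analysis?** The power calculation uses 100 participants, alpha 0.025, and standard deviations of 16 (USQ-NB items) and 4 (UTIs). None of these, and no model term, depends on item 10.

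**The case against.** The strongest reply is that this is an obvious slip with one sensible meaning. The literal reading would empty the candidate pool, so it could hardly be applied unnoticed, and the neighbouring 2-week items point to the likely intent. Nothing in the estimates, power or models depends on it. On that view it is an editorial correction.

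Most of this stands. The practical effect is probably small, and the point should not be presented as a threat to the results. What does not follow is that the text can be left alone: nothing in the document states the intended direction, and eligibility should not depend on staff silently reversing a criterion.

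A reader might infer that the description of the population directly contradicts item 10. It does not, for the reasons in step 4 of the working; the firm conflict is between item 10 and its lead-in. A reader might also infer that the enrolment records or the eligibility counts sent to the DSMB are wrong. The documents do not support that. They include no screening form and no account of how item 10 was applied, so a form could already carry the intended wording or omit the item. For the same reason, a special notice to the DSMB would be a matter of preference; correcting the text resolves the point.

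**Conclusion.** The point holds as a wording error in an operative eligibility rule, in four exclusion lists of four. It rests on reading the lead-in and item 10 as they stand, and on finding nothing elsewhere that fixes the direction. Identical wording and numbering in all four places make a text-extraction fault unlikely.

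Its size in people cannot be given: the documents do not say how many candidates have a recent neurologic change, or how screening staff read the item. That staff would reverse it is a judgement, though a likely one. A reader might go further and conclude that the trial would in fact enrol only people with a recent neurologic change, or that those enrolled are the wrong people. Nothing in the documents shows that the literal reading was or would be applied. The supported conclusion is narrower: as written, the rule points the opposite way to the other 2-week exclusions, and under the probable reading each stable enrollee meets a written exclusion.

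**What to change.** The sponsor should confirm the intended direction of item 10 and then reconcile it with the lead-in in the Phase Ia, 1b, II and III lists. If the intent is to keep out people with a recent change, there are two equivalent ways: reword the item as the event that excludes, or move the phrase about no change to the inclusion criteria. If any screening document repeats the wording, it needs the same correction.

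The cost is a one-line edit in each of four lists, plus the matching line in any such screening document. Sample size, power and analysis text stay as they are.
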